8.2.4. Surgical Evaluation of Specimen

Surgical evaluations of specimen, including ease of dissection, completeness of disease clearance, clot and vessel wall, are from perioperative measures (Visit 3).

Ease of dissection plane will be classed as easier than normal (1), normal (2), more difficult than normal (3); Completeness of disease clearance will be classed as better than expected (1), as expected (2), worse than expected (3); Both clot and vessel wall will be measured as score of 1 to 3 with the following scores: more solid than usual (1), normal (2) more friable than usual (3). The data will be treated as an ordinal response. A higher score means a worse case.

Surgical evaluations of specimen will be tabulated by treatment group for the PEA set containing the number and percentage of patients in each level. The Cochran Mantel-Haenszel test will be used to test the ordinal response difference between groups.

8.2.5. All-cause Death

All-cause death on or after randomisation will be tabulated by treatment group containing the number and percentage of patients with event for the PEA set and the PPS. All-cause death

during the whole study course, include deaths occurred during the screening period, will be captured in safety analyses.

Time from randomisation to death (in days) will be analysed using the Kaplan Meier method. Median and quartiles in days and associated 95% CI will be calculated using the LOGLOG transformation. All patients who are withdrawn or lost to follow-up prior to the end of the study, or who are still alive at the end of the study will be censored at the time of last contact, defined as the last reported visit date.

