4.3.2. PEA Set

The PEA set will consist of all ITT patients who actually undergo PEA. All analyses using the PEA set will group patients according to randomised treatment.

The PEA set will be used in efficacy analyses with assessments depending on the implementation of PEA.

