4.3.3. Per Protocol Set (PPS)

The PPS will consist of all ITT patients who fulfil all inclusion/exclusion criteria, have at least 80% overall dose compliance with study drug, have not taken any prohibited medication, have no significant protocol deviations, have valid PVR assessments at baseline (from patient history) and Visit 2, and undergo PEA as planned. All analyses using the PPS will group patients according to treatment actually received. A blind review of data will identify which patients will be included in the PPS.

The PPS will be used in the primary and secondary efficacy analyses as supportive analyses.

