7.2.2. Treatment Compliance

Patient compliance with study drug will be assessed by the investigator and/or study personnel at Visit 2 and during a telephone call using direct questioning and tablet counts. Deviations from the prescribed treatment regimen will be recorded on the source document and the patient's eCRF.

The overall treatment compliance (%) will be evaluated by calculating the number of tablets taken by the patient divided by the number of tablets expected to be used during the treatment period and multiplied by 100.

The number of tablets taken will be calculated by subtracting the number of tablets returned from the number of tablets dispensed. The number of tablets expected will be calculated by multiplying the total number of days of planned exposure to study drug (treatment duration) by the number of tablets planned per day (3 tablets per day).

The overall treatment compliance (%) will be summarised using descriptive statistics.

A patient is considered compliant if overall treatment compliance is greater than or equal to 80%. A categorical summary of whether patients were compliant (yes/no) will be present. The number and percentage of patients in compliance category of <80%, >=80 and <=120%, and >120% will also be presented.

By-patient listing will be provided to support the summary table.

8. Efficacy Analysis

The primary analysis will use ITT set, all analyses on perioperative endpoints will use PEA set only; all analyses on postoperative endpoints will use PEA set and PPS. For other endpoints, the analysis set to be used is specified in each subsection below. By-patient listings will be provided to support the summary tables.

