8.2.2. Composite Clinical Endpoints

Composite clinical endpoints from randomisation to Visit 4 will be tabulated by treatment group containing the number and percentage of patients with an event as well as the number of event for the PEA set and the PPS. The Fisher exact test will be utilised to test the proportion difference along with the Clopper-Pearson exact CI when applicable. For analysis based on the ordinal response of functional class, the row mean score from the Cochran Mantel-Haenszel test will be used to test the response difference between groups.

Composite clinical endpoints include following clinical endpoints:

- All-cause death

All deaths that happen after randomisation until the date of Visit 4, 6 months after the PEA, will be included.

- PH-related hospitalisation

All PH-related hospitalisation except the in-hospital care after PEA from randomisation until 6 months after PEA will be included.

- Need for PAH-targeted therapy

All PAH-targeted therapy from randomisation until 6 months after PEA will be included.

- Functional class unchanged or worse

When comparing the functional class assessment at Visit 1 with the functional class assessment at other visits, the same class will be defined as unchanged, and a higher class will be defined as worse. The worst case after treatment will be used.

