9.5. Physical Examination

A complete physical examination including assessments of the head, eyes, ears, nose, throat, skin, neck (including thyroid), lungs, cardiovascular system, abdomen, lymph nodes, and extremities will be obtained at screening. A physical examination including updates since the screening visit with focus on previously noted abnormalities in organ systems, including skin and hair, will be completed at time points specified in Schedule of Events.

Physical examination data will be summarised by treatment group and body system with number and percentage of patients.

Physical examination results for all patients will be presented in a listing.

10. Interim Analysis

A data safety monitoring board (DSMB) will review unblinded safety data throughout the study and make recommendations as appropriate. Further details are specified in the DSMB charter.

11. Changes in the Planned Analysis

The changes for the statistical analyses from the protocol to this SAP are stated below:

1. The analysis set to be used for perioperative endpoints (Circulatory Arrest Time, Surgery-related Complications, Surgical Evaluation of Specimen, PEA hospital length of stay, PEA ICU length of stay, Time on mechanical ventilation, In-hospital mortality) have been updated to PEA set only, with the consideration that these endpoints are peri-PEA surgery related endpoints and it makes more sense to narrow down the patients to those who have undergone PEA surgery only.
2. The analysis sets to be used for postoperative endpoints (Percent Change in PVR from baseline to Visit 4, Composite clinical endpoint from baseline to Visit 4, NT-proBNP, cardiac output, cardiac index, mRAP, mPAP, PAWP change from baseline to Visit 4, Functional class at Visit 4, All-cause death, Need for PAH-targeted postoperative therapy at Visit 4) have been updated to PEA set and PPS, with the consideration that the endpoints are post-PEA surgery endpoints, and it makes more sense to restrict the analysis to patients who undergone PEA surgery; PPS will be used since those per-protocol patients need to be considered as a complementary analysis set.

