3. The analysis defined in the protocol “For laboratory data, the proportion of patients with clinically significant abnormal values as reported by the investigator will be provided by laboratory parameter, dose cohort, and scheduled visit.” Will be removed since it is confirmed by central labs that the data on ‘clinically significant/non-clinically significant’ will not be obtained.
4. The observation period for composite endpoints as now defined in section 8.2.2 has been changed to ‘from randomisation to Visit 4’ instead of ‘from PEA to Visit 4’ since it is of more interest to investigate the endpoints from randomization;
5. The exploratory endpoint ‘Need for PAH-targeted postoperative therapy at the 6-month visit (Visit 4)’ in the protocol has been changed to ‘Need for PAH targeted postoperative therapy from immediately after PEA to Visit 4’ since it is of more interest to see if PAH targeted therapy occurs from PEA till Visit 4.

The surgical evaluation of specimen is from perioperative measurement (Visit 3), according to the new text of Appendix 1 in Protocol Amendment 1.

12. References

1. Investigator's Brochure V18.0 23Feb18, Section "5.4.2 Exposure Information".

13. Appendices

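### All-cause death and the clinical composite are counted from randomisation, but only in sets that require PEA, so pre-PEA deaths and composite events in patients who never reach PEA cannot be counted

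*SAP*

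**What the plan says.** **Event windows.** For all-cause death, SAP 8.2.5 reads: "death on or after randomisation will be tabulated by treatment group containing the number and percentage of patients with event for the PEA set"; it names the PPS as well. It adds that "Time from randomisation to death (in days) will be analysed using the Kaplan Meier method", without naming a set. SAP 8.2.2 states: "Composite clinical endpoints from randomisation to Visit 4 will be tabulated by treatment group containing the number and percentage of patients with an event", again for the PEA set and the PPS.

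**Analysis sets.** SAP 4.3.2: "The PEA set will consist of all ITT patients who actually undergo PEA". SAP 4.3.3 requires PPS patients to "have valid PVR assessments at baseline (from patient history) and Visit 2, and undergo PEA as planned". The opening of SAP 8 says that "all analyses on postoperative endpoints will use PEA set and PPS".

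**Declared changes (SAP 11).** Item 2 lists the composite and all-cause death among the postoperative endpoints and gives as its reason that "it makes more sense to restrict the analysis to patients who undergone PEA surgery". Item 4 moves the start of the composite from PEA to randomisation, "since it is of more interest to investigate the endpoints from randomization".

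**Text that points the other way.** SAP 4.3.1 and Protocol 7.6 both make the ITT set (all dosed patients, grouped as randomised) the main set for secondary efficacy. Protocol 7.2 item 5 defines the death endpoint as covering every death over the whole study. SAP 8.2.5 sends deaths over the whole study, including those during screening, to the safety analyses. SAP 9.1.6 then provides a summary of fatal TEAEs and a listing of all deaths.

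**The concern.** The endpoint starts at randomisation, but a patient enters the analysis only by surviving to surgery and having it, about three months later. Reaching PEA is a post-randomisation outcome. Riociguat could change it in either direction, by stabilising patients or by causing harm or withdrawal before surgery. Restricting death and the composite to patients who had PEA conditions both comparisons on that outcome and gives up the protection of randomisation.

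The part of follow-up that loses its deaths is also the period when study drug is taken. An excess of pre-PEA deaths in one arm would be invisible in the secondary death analysis. Failure to reach surgery after a PH-related hospitalisation or the start of PAH-targeted therapy would be invisible in the composite.

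**Working it through.** **1. What the sets allow.**

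| Patient | Death table (8.2.5) | Composite (8.2.2) |
|---|---|---|
| Dies before PEA | not counted | not counted |
| Non-fatal event before PEA, later has PEA | – | counted |
| Non-fatal event, never has PEA | – | not counted |
| Event after PEA | counted | counted |

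The last two columns describe the PEA set; the PPS is a narrower set with the same surgery condition. The number of pre-PEA deaths these analyses can count is therefore 0 by definition.

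**2. Kaplan-Meier analysis.** No set is named. The opening of SAP 8 and SAP 11 item 2 imply the PEA set and PPS; this is an inference. If so, every patient is certain to survive to PEA. On the nominal schedule (PEA about Day 96, Visit 4 at Day 276) that covers 96/276 = 35% of follow-up.

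**3. How many deaths could be excluded.** The plan states no pre-PEA event rate, so there is no figure to reproduce. A rough anchor from a different population is the CTEPH extension study in Protocol 1.4 (33 deaths in 237 patients, mean 1165.4 days):

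- Patient-years: 237 × 1165.4 / 365.25 = 756.2
- Rate: 33 / 756.2 = 0.0436 per year
- Risk by Day 96: 1 − exp(−0.0436 × 96/365.25) = 1.14%
- Expected in 88 patients: 88 × 0.0114 = 1.0
- Chance of at least one: 1 − (1 − 0.0114)^88 = 0.64

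| Assumed pre-PEA mortality | Expected deaths in 88 | Chance of at least one |
|---|---|---|
| 1% | 0.9 | 0.59 |
| 2.5% | 2.2 | 0.89 |
| 5% | 4.4 | 0.99 |

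The planned 10% dropout (8.8 of 88) is only a ceiling for patients outside the PEA set. Protocol 4.3.3 counts dropout up to Visit 4, so the ceiling would be reached only if all of it came before PEA.

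**4. Effect on the death comparison.** Assume 44 dosed per arm and 2 post-PEA deaths per arm (44 × the cited 4.7% perioperative mortality = 2.1).

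| Pre-PEA deaths | PEA set | ITT set |
|---|---|---|
| 1 v 0 | 2/43 (4.7%) v 2/44 (4.5%) | 3/44 (6.8%) v 2/44 (4.5%) |
| 4 v 0 | 2/40 (5.0%) v 2/44 (4.5%) | 6/44 (13.6%) v 2/44 (4.5%) |

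In the second row the difference is 0.5 points in the PEA set and 9.1 points in the ITT set (Fisher p = 0.27 for ITT).

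**5. Effect on the composite.** Assume 12 events per arm among PEA patients, and 4 v 0 patients who have an event but never reach PEA.

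- PEA set: 12/40 (30.0%) v 12/44 (27.3%), difference 2.7 points, Fisher p = 0.81
- ITT set: 16/44 (36.4%) v 12/44 (27.3%), difference 9.1 points, Fisher p = 0.49

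**6. Estimability of the Kaplan-Meier summaries.** SAP 8.2.5 asks for the median and quartiles. The first quartile needs about 25% mortality, roughly 11 of 44. The binomial probability of 11 or more deaths in 44 is 4.5 × 10⁻⁶ at 4.7% mortality and 0.003 at 10%.

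**The case against.** **Deaths are not lost from the report.** SAP 8.2.5 itself sends whole-study deaths to the safety analyses. SAP 9.1 and 9.1.6 give fatal TEAEs by arm and a listing. SAP 5.1 tabulates discontinuation with death as a reason in the ITT set, and SAP 8.2.6 tabulates pre-PEA withdrawals in the ITT set. The safety and ITT sets have the same members unless someone received the wrong treatment, and no test is specified for the death table. This stands: counts of pre-PEA deaths by arm can be recovered. What cannot be recovered from any specified table is time to death by randomised group, or the composite in patients who never reach PEA.

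**The large examples are extreme.** At 1.14% pre-PEA mortality, a split of 4 or more v 0 in either direction has a probability of about 0.2%; at 5%, about 4%. Exclusion criterion 1 also removes unstable patients who need urgent surgery. The composite base rate of 12 per arm has no source. With unchanged functional class counting as an event, rates could be much higher: at 36/40 v 40/44, four added events shift the difference by only 0.9 points. This also stands. The examples show how the estimate can move, not what to expect.

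**The 35% event-free time is not a separate bias.** It restates the conditioning on PEA, and it depends on the inferred set. That is fair, and the set should be named for that reason.

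**Another consistent remedy exists.** The clock could start at PEA, as the Protocol 7.2 composite heading does. That would resolve the mismatch but would still compare only patients selected after randomisation, and SAP 11 item 4 states a wish to look from randomisation.

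**The analyses are exploratory and the change is declared.** Both are true. But the reason declared in item 2, that these are post-surgery endpoints, does not fit a composite that item 4 starts at randomisation.

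**Conclusion.** The concern holds and should be fixed; it does not affect the primary endpoint. The exclusion follows from the set definitions alone and needs no assumption. The Kaplan-Meier part rests on an inference about which set is meant. SAP 8, 8.2.2, 8.2.5 and 11 item 2 conflict with SAP 4.3.1, SAP 11 item 4, Protocol 7.2 item 5 and Protocol 7.6.

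The size is unknown. About one excluded death among 88 patients is a reasonable central figure if the extension-study rate carries over, and 0.9 to 4.4 if pre-PEA mortality is 1% to 5%. In the examples worked here the distortion shows in the estimate rather than in a changed test result. The composite is the more exposed endpoint, because no other table stands in for it.

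**What to change.** In SAP 8, 8.2.2, 8.2.5 and 11 item 2:

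- Make the ITT set the main set for all-cause death, time to death and the composite, and name the set for the Kaplan-Meier analysis.
- Keep the PEA set and PPS as supportive analyses, start their clock at PEA, and label them as conditional on surgery.
- For patients without PEA, end the window at the scheduled Visit 4 day (Day 276). Protocol 4.3.2 already asks, where possible, for Visit 4 assessments after discontinuation.
- For functional class in patients without PEA, use the available post-baseline assessments without the rule that Visit 2 data are valid only within 7 days before PEA. Judge a patient with no such assessment on the other components, and add a sensitivity analysis that counts that patient as an event.
- Report the Kaplan-Meier survival probability at Visit 4 with a 95% CI by arm instead of the median and quartiles.
- Leave the Visit 2 endpoints in 8.3 unchanged.

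The set change is the essential step. The Day 276 window and functional-class rule are open to debate, and ascertainment may be less complete without PEA.

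The cost is SAP text and a few tables before database lock, with no new data collection. The set returns to the one in Protocol 7.6; the rules for patients without PEA are new text. One limit remains: the ITT set contains dosed patients only, so a death between randomisation and first dose would still be missed and should be listed.

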8.2.6. Withdrawal during Randomised Treatment Phase

Withdrawal during the randomised treatment phase along with the reason for withdrawal will be tabulated by treatment group for the ITT set and the PPS containing the number and percentage of patients with event. Only withdrawals after randomisation but before PEA will be included.

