4.2 Assessment of Exclusion Criteria

The exclusion criteria related to laboratory assessments:

- Has known active hepatitis A immunoglobulin M, hepatitis B surface antigen, or hepatitis C antibody;
- Is human immunodeficiency virus positive;
- Has creatinine clearance <15 mL/min or is on any form of dialysis

will be assessed from patient history when the last assessment of these criteria occurred not more than or equal to 180 days before Visit 1.

If the last assessment occurred more than 180 days ago, laboratory assessments for these criteria will be performed on V0. Patients will be instructed to either represent for V1 or, when V0 and V1 are held on the same day, to initiate study drug when the laboratory results are available and the patient eligibility has been confirmed. In the latter cases, eligibility will be communicated to the patient by telephone call.

Laboratory assessments of these criteria, and a serum pregnancy test (if applicable), will be performed as confirmation at Visit 1 in all cases.

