7.6 Analysis Sets

The following analysis sets will be used in the statistical analyses.

Intent-to-treat (ITT) set: The ITT set will consist of all participants who received at least one dosage of randomised study drug. All analyses using the ITT will group participants according to randomised treatment.

PEA set: The PEA set will consist of all ITT participants who actually undergo PEA. All analyses using the PEA will group participants according to randomised treatment.

Per-protocol set (PPS): The PPS will consist of all ITT participants who fulfil all inclusion/exclusion criteria, have at least 80% overall dose compliance with study drug, have not taken any prohibited medication, have no significant protocol deviations, have valid PVR assessments at baseline and Visit 2, and undergo PEA as planned. All analyses using the PPS will group participants according to treatment actually received. A blind data review of data will identify which participants will be included in the PPS.

Safety set: The safety set will consist of all participants who received any study drug. All analyses using the safety set will group participants according to treatment actually received.

The ITT set will be used as the primary efficacy analysis set including primary, secondary, and exploratory efficacy analyses.

The PPS will be used in the primary and secondary efficacy analyses as supportive analyses. The exploratory efficacy analyses may use PPS in a way more relevant to the specific question, which is specified in the SAP.

The safety set will be used in safety analyses.

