If the last assessment occurred more than 180 days ago, laboratory assessments for these criteria will be performed on V0. Patients will be instructed to either represent for V1 or, when V0 and V1 are held on the same day, to initiate study drug when the laboratory results are available and the patient eligibility has been confirmed. In the latter cases, eligibility will be communicated to the patient by telephone call.

Laboratory assessments of these criteria, and a serum pregnancy test (if applicable), will be performed for confirmation at Visit 1 in all cases.

Rationale for change

Please refer to the rationale for change for Appendix 1, Schedule of Events

5. Section 7.6 Analysis set (page 57)**Old text**

The ITT set will consist of all participants who were randomly assigned to receive double-blind study drug.

New text

Intent to treat (ITT) set : The ITT set will consist of all participants who received at least one dosage of randomised study drug. All analyses using the ITT will group participants according to randomised treatment.

Rationale for change

Study drug intake can only occur once all inclusion and exclusion criteria are confirmed. In a minority of instances, patients may be randomised while laboratory assessments are ongoing. In the interest of an unbiased ITT population, only patients with at least one study drug dosage will be included in the ITT analysis set.

6. Administrative changes**Section 5.4.1, Study Drug Packaging and Storage (page 39)****Old text**

Riociguat tablets and matching placebo tablets will be packed in aluminium foil blisters in cartons and shipped by PPD Global Clinical Supplies.

New text

Riociguat tablets and matching placebo tablets will be packed in high-density polyethylene bottles and shipped by PPD Global Clinical Supplies.

Section 7.3, Exploratory Efficacy Endpoints (page 57)**Old text**

Need for PAH-targeted preoperative therapy at the 6-month visit (Visit 4)

New text

Need for PAH-targeted postoperative therapy at the 6-month visit (Visit 4)

Section 6.3.2 and 7.8.4, Vital signs (pages 50 and 61)**Old text**

Vital signs, including blood pressure, pulse rate, respiration, and body temperature will be obtained with the patient in a seated position after resting for approximately 5 minutes.

For vital sign measurements, supine blood pressure and HR (absolute values and change from baseline) will be summarised by dose cohort and scheduled visit.

New text

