4.3.1. Intent-to-Treat (ITT) Set

The ITT set will consist of all patients who received at least one dosage of randomised study drug. All analyses using the ITT set will group patients according to randomised treatment.

The ITT set will be used as the primary efficacy analysis set including primary, secondary, and exploratory efficacy analyses.

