5.1. Disposition

Patient disposition will be summarised by treatment group for the ITT set, unless otherwise specified.

The number and percentage of patients in each analysis set defined in Section 4.3 will be tabulated. The number and percentage of patients entered each scheduled visit will also be tabulated.

Patients who completed the study, patients who discontinued from the study and reasons of discontinuation will be tabulated using the frequency counts and percentages.

The reasons for patients not completing the study will be recorded on eCRF with the following categories: Adverse Event, Death, Lack of Efficacy, Lost to Follow-up, Non-Compliance with Study Drug, Physician Decision, Pregnancy, Progressive Disease, Protocol Violation, Recovery, Trial Screen Failure, Study Terminated by Sponsor, Technical Problem, Withdrawal by Subject, and Other.

Patient enrollment data and reasons for screen failure will be presented in a listing. Patient disposition data, including reasons for study discontinuation, will also be provided in a listing.

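### Withdrawal before PEA is counted from randomisation but tabulated in the PPS and in a dosed-only ITT set, neither of which fits that window

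*SAP*

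**What the plan says.** Withdrawal during the randomised treatment phase is a named secondary efficacy endpoint (protocol 7.2, SAP 3.2.2). SAP 8.2.6 sets the window: "Only withdrawals after randomisation but before PEA will be included". It then says that withdrawals, with their reasons, "will be tabulated by treatment group for the ITT set and the PPS containing the number and percentage of patients with event".

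The two sets are defined as follows.

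- **PPS (SAP 4.3.3).** Among other conditions, members must "have valid PVR assessments at baseline (from patient history) and Visit 2, and undergo PEA as planned".
- **ITT (SAP 4.3.1).** "The ITT set will consist of all patients who received at least one dosage of randomised study drug". Protocol 7.6 has the same rule: "The ITT set will consist of all participants who received at least one dosage of randomised study drug".

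The protocol allows an interval between randomisation and first dose. Under protocol 4.2, when screening and randomisation fall on one day and the eligibility laboratory tests are more than 180 days old, the patient is told "to initiate study drug when the laboratory results are available and the patient eligibility has been confirmed". The rationale for Amendment 1, in protocol Appendix 3, says: "In a minority of instances, patients may be randomised while laboratory assessments are ongoing".

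On disposition, SAP 5.1 says: "Patient disposition will be summarised by treatment group for the ITT set, unless otherwise specified".

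**The concern.** The endpoint's clock starts at randomisation and stops at PEA. One analysis set admits only patients who reach PEA. The other admits patients only from their first dose. Followed to the letter, the plan yields one table that carries no information and one that cannot show the earliest part of the endpoint's own window.

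What is at stake is the reporting of a secondary endpoint. A PPS table showing no withdrawals in either arm could be taken for a finding. Patients who were randomised and never dosed would also have no row by arm in any planned table, although a reader needs that count to follow the flow from randomisation to analysis.

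**Working it through.** **1. The plan's own figure.** Protocol 4.3.3 gives 88 randomised, 80 completers and 10% dropout. 80 × 1.10 = 88 exactly; 80 / (1 − 0.10) = 88.9, rounded up to 89. The figure reproduces and is not in dispute. It is stated per randomised patient, and dropout there runs to Visit 4, not only to PEA.

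**2. PPS against the event window.**

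- Event: the patient leaves the study after randomisation and before PEA.
- PPS membership: dosed, valid Visit 2 PVR, PEA undergone as planned.
- A Visit 2 assessment is valid only if made within 7 days before PEA (SAP section 4 and 8.1).

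Take it that a patient who leaves the study before PEA has no PEA within the study. Then no combination of dosing, PEA and Visit 2 status puts that patient in the PPS. The row is 0/n in each arm whatever happens in the trial.

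**3. ITT against the event window.**

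- A patient randomised with results pending may prove ineligible, and failing the entry criteria is the first withdrawal reason in protocol 4.3.1. That withdrawal falls inside the endpoint window.
- With no dose taken, the patient is outside the ITT set. The PEA set and PPS are subsets of ITT (SAP 4.3.2, 4.3.3), and the safety set also needs a dose (SAP 4.3.4).
- SAP 5.1 tabulates the sets of section 4.3, none of which is all randomised patients. SAP section 11 changes the sets for perioperative and postoperative endpoints but does not mention this one.

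**4. Possible size.** The documents give no number of undosed patients, so the counts below are assumptions. Let W be withdrawals before PEA among 88 randomised, and k the number of those before first dose, with no other undosed patients. The endpoint definition gives W/88; the ITT table gives (W − k)/(88 − k).

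| W | W/88 | k = 0 | k = 1 | k = 2 | k = 4 |
|---|---|---|---|---|---|
| 4 | 4.5% | 4/88 = 4.5% | 3/87 = 3.4% | 2/86 = 2.3% | 0/84 = 0.0% |
| 8 | 9.1% | 8/88 = 9.1% | 7/87 = 8.0% | 6/86 = 7.0% | 4/84 = 4.8% |
| 12 | 13.6% | 12/88 = 13.6% | 11/87 = 12.6% | 10/86 = 11.6% | 8/84 = 9.5% |

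W = 8 equals the whole planned loss to Visit 4 (88 − 80 = 8), so it is a generous value for losses before PEA. When k is 0 the two denominators agree; otherwise the ITT figure is the lower one. These figures pool the arms, whereas the planned table is by arm.

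**The case against.** **The PPS zero rests on a reading of withdrawal.** SAP 8.2.6 does not say whether it means leaving the study or stopping study drug, and protocol 4.3.2 speaks of both. A patient who stops drug early could still have a valid Visit 2 catheterisation and PEA. Compliance need not exclude that patient, because the expected tablet count in SAP 7.2.2 uses treatment duration, which SAP 7.2.1 measures from first to last dose. This stands: a reader might infer that the PPS row is zero under any reading, and the documents do not support that. Protocol 6.2.9 and SAP 5.1 favour withdrawal from the study, so the point holds on the likelier reading.

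**The PPS table follows a general rule and does little harm.** Protocol 7.6 makes the PPS supportive for all secondary endpoints, the ITT table sits beside it, and no test is planned. That is fair, and it limits the consequence. It does not make the table informative.

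**Undosed patients are not lost.** A reader might infer that they vanish from the report. They do not: SAP section 4 promises by-patient listings for all screened patients, and SAP 5.1 lists disposition with reasons. They are listed but not tabulated.

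**The dosed-only ITT set was deliberate.** Amendment 1 explains it, and calls randomisation with results pending a minority of instances. In a double-blind trial, withholding the first dose because of pre-dose laboratory results cannot be an effect of treatment. A reader might infer that the ITT definition is itself an error, or that it biases the primary comparison. Neither inference is supported. What remains is a mismatch between that set and an endpoint counted from randomisation.

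**Conclusion.** The point holds as a mismatch between one secondary endpoint and its analysis sets. On the reading that withdrawal means leaving the study, the PPS table is 0/n in both arms by construction. The ITT table omits any withdrawal between randomisation and first dose, and disposition does not recover it.

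The size cannot be known from the documents. With 8 withdrawals before PEA among 88 randomised, 0 to 4 of them before first dose, the ITT table would show between 9.1% and 4.8% against 9.1% under the endpoint's definition. The lower end needs half of all withdrawals to precede the first dose, and undosed patients are expected to be few. Whether any event is omitted at all is open. The endpoint is descriptive and the study's analyses are exploratory, so the consequence is for reporting.

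**What to change.** - **SAP 8.2.6:** state that withdrawal means withdrawal from the study. Delete the PPS. Tabulate withdrawals over all randomised patients by randomised arm, split into before first dose and first dose to PEA, with reasons.
- **SAP 5.1:** add, by arm, the number randomised and the number randomised but not dosed, with reasons.
- **SAP section 11:** record the change, since protocol 7.6 assigns the ITT set and the PPS to secondary endpoints.

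The dosed-only ITT set stays as it is for the other efficacy analyses. The cost is SAP wording and one or two changed descriptive tables. No new data are needed, because randomisation is administered through the IWRS.
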